12.4.6 Protocol Deviations Due to an Emergency or Adverse Event

Departures from the protocol will be determined as allowable on a case-by-case basis and only in the event of an emergency. The Investigator or other physician in attendance in such an emergency must contact the Medical Monitor as soon as possible to discuss the circumstances of the emergency.

The Medical Monitor, in conjunction with the Investigators, will decide whether the patient should continue to participate in the study. All protocol deviations and corresponding remediation plan will be tracked in the TRIO Clinical Trial Management System.

Period of Observation:

The table below summarizes the different periods of observation of AE, SAE, AESI with Atezolizumab and Pregnancy/Lactation.

Type of Event	AE	SAE	AESI with Atezolizumab	Pregnancy/Lactation
Reporting period	From consent until 30 days after the end of the treatment	From consent until 90 days after the last dose of study treatment for all SAEs, and any time after the end of study for SAEs believed related to entinostat or the combination	From consent until 90 days after the last dose of study treatment, or 30 days after the initiation of a new anticancer therapy, whichever is earlier	From consent until 120 days after the last dose of study treatment or 30 days following the discontinuation of the study treatment in case of the start of a new anticancer therapy Note: all patients becoming pregnant must be followed up

				to the completion / termination of the pregnancy.
Reporting Timelines to the Sponsor	Entered into the clinical database on an ongoing basis	Within 24 hours	Within 24 hours	Within 24 hours

12.5 Safety Monitoring

The safety and tolerability of the investigational treatments will be monitored throughout the course of the study by the Investigator and the Medical Monitor. Additionally, an independent data safety monitoring board (DSMB) will be established for the Phase 2 portion of this study to act in an advisory capacity to the Sponsor with respect to safeguarding the interests of trial patients and assessing the safety of the interventions administered during the trial.

The safety and tolerability data that will be reviewed by the Medical Monitor and DSMB will include, but are not limited to, adverse events, laboratory test results, and patient discontinuations. Additionally, the development of serious adverse events will be assessed by the Medical Monitor and DSMB on a continuous basis. Note: All serious adverse events must be reported to the Sponsor within 24 hours of discovery or notification of the event. No formal safety stopping rules are specified in the protocol. However, if any significant safety issues arise, a decision to modify or terminate the trial will be made by the Sponsor in collaboration with the DSMB and the study's Steering Committee.

13. STATISTICAL CONSIDERATIONS

13.1 Sample Size Estimation

13.1.1 Dose Determination Phase

Three to 6 patients will be enrolled in each dose cohort based on a standard Phase 1 dose-finding scheme. The total number of patients to be enrolled in the dose determination phase is dependent upon the observed safety profile, which will determine the number of patients per dose cohort, as well as the number of dose adjustments required to achieve either the MTD or the recommended Phase 2 dose. Therefore between 6 and 18 patients will be included in the Dose Determination Phase 1 part. Note: patients who discontinued the study for reasons other than study drug related toxicities before completing cycle 1 may be replaced.

A starting sample size of 3 evaluable patients per dose cohort, expanding to 6 in the event of a marginal DLT rate (33%) was deemed to be a safe and conventional approach in dose-finding. Assuming a true DLT rate of 5% or less, there would be a 3% chance that dose escalation would be halted in a given cohort (i.e., observing 2 or more patients with DLT). If a true DLT rate of 50% is assumed, then there would be an 83% chance that dose escalation would be halted in a given cohort.

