Phase 1b (Dose Determination): This study phase employs a classical 3+3 design, with the determination of DLT and the MTD or RP2D based on the combination of entinostat with atezolizumab in C1. Six patients will need to be treated in a dose level for it to be considered MTD or the RP2D. The recommended dose for Phase 2 investigation will be the higher of either 2, 3 or 5 mg weekly PO that results in less than a 33% incidence of DLT. The final determination of the optimal dose for further use will consider both acute and cumulative toxicities; the incidence of required dose delays, reductions, and discontinuations; and the overall facility of administration in clinical practice.

The initial 3-6 patients will receive entinostat at a starting dose of 5 mg (Dose Group 1) on D1, D8, and D15 along with atezolizumab 1200 mg via intravenous (IV) infusion on D1 of each 21-day cycle.

If the 5 mg dose exceeds the MTD, then a 3 mg dose of entinostat (Dose Group -1) will be evaluated in the same manner. If the -1 dose level exceeds the MTD, then a 2 mg dose of entinostat (Dose Group -2) will be evaluated. Based on evaluation of the safety and tolerability data gathered during the dose determination phase together with data from other clinical trials, it may also be decided that accrual will take place at an alternate dose level or dosing schedule via a protocol amendment.

Patients who experience a DLT will be allowed to remain on study if they meet the following criteria; (1) the investigator believes it is appropriate for patients to remain on study (2) the event has resolved and no longer meets the definition of DLT and (3) the timeline for resolution falls within the guidelines for dose delays ([Section 9.10](#)).

Phase 2 (Expansion): The efficacy and safety of entinostat in combination with atezolizumab will be evaluated using the RP2D identified in the Dose Determination Phase. In this randomized, placebo-controlled, double-blind study phase, 70 patients will be randomized in a 1:1 fashion to atezolizumab + entinostat versus atezolizumab + placebo. The randomization will be stratified by geographic location (US vs. rest of world).

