6.3 Number of Patients

Phase 1b Dose Determination Phase: Up to 18 patients may be enrolled. In this phase, up to 3 doses of entinostat will be explored in a standard “3+3” Phase 1 dose finding scheme. Six patients will need to be treated in a dose level for it to be considered MTD or the RP2D.

Entinostat dosing will start at 5 mg po weekly and then decrease to 3 mg weekly in the case that the 5 mg weekly dose leads to ≥ 2 DLTs. It will again be de-escalated to 2 mg weekly should the 3 mg weekly dose lead to ≥ 2 DLTs. Each patient will be counted in only 1 dose cohort. Thus, the total number of patients to be enrolled in the Dose Determination Phase is dependent upon the observed safety profile, which will determine the number of patients per dose cohort, as well as the number of dose de-escalations required to achieve the MTD.

Note: The patients who discontinued the study for reasons other than study drug related toxicities before completing Cycle 1 may be replaced.

In the Phase 2 Expansion Phase, a total of 70 TNBC patients are planned to be enrolled for evaluation (35 patients per arm). Note: It is anticipated that the number of patients who will drop out of the study without PFS failure beforehand will be low (expected to not exceed 2–3%). Depending on the actual number of such dropouts, the number of patients accrued may be increased by 6–10 additional patients to accommodate for a higher-than-expected number of dropouts.

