5.2 Sample Size

5.2.1 Phase 1b Dose Determination Phase

Three to six patients will be enrolled in each dose cohort based on a standard Phase 1 dose-finding scheme.

A starting sample size of 3 evaluable patients per dose cohort, expanding to 6 in the event of a marginal DLT rate (33%) was deemed to be a safe and conventional approach in dose-finding. Assuming a true DLT rate of 5% or less, there would be a 3% chance that dose escalation would be halted in a given cohort (i.e. observing 2 or more patients with DLT). If a true DLT rate of 50% is assumed, then there would be an 83% chance that dose escalation would be halted in a given cohort.

6 patients will need to be treated in a dose level for it to be considered as MTD or RP2D.

**Statistical Analysis Plan
SNDX-275-0602 (TRIO025)
DM-025-037**

Patients who discontinued the study for reasons other than study drug related toxicities before completing Cycle 1 will be replaced.

Therefore, between 6 and 18 patients will be included in the Dose Determination Phase.

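### The quoted 83% chance of halting at a 50% DLT rate fits a 3+3 that clears a dose at 0 of 3; under the plan's six-patient acceptance rule the chance is 89%

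*Protocol*

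**What the plan says.** Protocol 13.1.1 gives two operating characteristics for a Phase 1b cohort. At the low end: "Assuming a true DLT rate of 5% or less, there would be a 3% chance that dose escalation would be halted in a given cohort", where halting is explained as "observing 2 or more patients with DLT". At the high end, for a true DLT rate of 50%, "then there would be an 83% chance that dose escalation would be halted in a given cohort". The Protocol synopsis (Sample Size Considerations) carries the same two figures, and SAP 5.2.1 repeats the second: "there would be an 83% chance that dose escalation would be halted in a given cohort".

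The sentence just before these figures describes how a cohort grows: "A starting sample size of 3 evaluable patients per dose cohort, expanding to 6 in the event of a marginal DLT rate (33" (the bracketed figure is 33%). Protocol 6.1 labels the design in the same spirit: "This study phase employs a classical 3+3 design".

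Elsewhere the plan sets a stricter condition for accepting a dose:

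- Protocol 6.3: "Six patients will need to be treated in a dose level for it to be considered MTD or the RP2D". The synopsis, Protocol 6.1, SAP 3.1 and SAP 5.2.1 say the same.
- Protocol 9.7 and SAP 6.8 define the MTD by a DLT proportion below 33% among 6 patients.
- The synopsis opens Phase 2 when fewer than 2 of 6 patients in a cohort have a DLT.
- Protocol 13.1.1 and SAP 5.2.1 give the Phase 1b size as 6 to 18 patients.
- Dosing starts at 5 mg, the highest planned level. It moves to 3 mg and then 2 mg only if the level above produces 2 or more DLTs (Protocol 6.3).

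**The concern.** The 83% and the acceptance rule describe different schemes. In an escalating 3+3, 0 DLTs in 3 patients ends the cohort, because the next patients go to a higher dose. Here no higher dose is planned: 5 mg is the top level, and 3 mg and 2 mg are reached only after the level above has failed. If six treated patients are needed before a dose can be MTD or RP2D, a cohort with 0 of 3 cannot be accepted at that point and must also go to six. The path that the 83% counts as a pass at three patients would then still be open to failure.

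At stake is whether the probabilities quoted beside the Phase 1b cohort size belong to the rule by which a dose will be accepted or rejected. They are the only figures offered on how the dose-finding phase performs. The text also gives the chance that escalation is halted, although no planned step goes up.

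**Working it through.** **Inputs.** True DLT rates of 5% and 50%, and failure at 2 or more DLTs (Protocol 13.1.1). The expansion sentence in the same section. The six-patient requirement (Protocol 6.3), the MTD definition (Protocol 9.7) and the Phase 2 gate (synopsis). The 33% rate in the table takes p = 0.33 and is added for illustration. Write X for the number of DLTs in a group of patients with DLT probability p.

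**Step 1: reproduce the plan's figures (expand only after 1 of 3).**

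P(fail) = P(X ≥ 2 of 3) + P(X = 1 of 3) × P(X ≥ 1 of next 3)

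- p = 0.50: 0.500 + 0.375 × 0.875 = 0.828, the stated 83%.
- p = 0.05: 0.00725 + 0.1354 × 0.1426 = 0.0266, the stated 3%.

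Both figures reproduce.

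**Step 2: the six-patient rule.** A dose is accepted only with 0 or 1 DLT in 6, so

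P(fail) = P(X ≥ 2 of 6) = 1 − (1 − p)^6 − 6p(1 − p)^5

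- p = 0.50: 1 − (1 + 6)/64 = 57/64 = 0.891.
- p = 0.05: 0.0328, which still rounds to 3%.

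Stopping a cohort at the second DLT does not change these values, since the cohort has already failed.

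**Step 3: where the gap comes from.** It is exactly the path of 0 of 3 followed by 2 or more of the next 3. At p = 0.50 this is 0.125 × 0.500 = 0.0625, and 0.828 + 0.0625 = 0.891.

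| True DLT rate | Expand only after 1 of 3 | Six patients required | Difference |
|---|---|---|---|
| 5% | 2.7% | 3.3% | 0.6 points |
| 33% | 56.6% | 64.2% | 7.7 points |
| 50% | 82.8% | 89.1% | 6.25 points |

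**Step 4: which scheme the size range fits.** If 0 of 3 cleared a dose, Phase 1b could end after 3 patients at 5 mg. The stated lower limit of 6 requires that a cohort with 0 of 3 also be filled to six. The upper limit is 3 levels × 6 patients = 18. Section 13.1.1 therefore takes its size range from one scheme and its probability from the other, and SAP 5.2.1 does the same.

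**The case against.** The strongest reply is that nothing has been miscalculated. The sentence beside the figure says that a cohort expands at a marginal DLT rate, Protocol 6.1 calls the design a classical 3+3, and for that scheme 83% is right. This stands. A reader might infer an arithmetic slip, but the documents do not support that: both stated figures reproduce. The fault is a mismatch between two descriptions of when a cohort goes to six. Changing 83% to 89% alone would leave a figure that no longer matched the sentence before it.

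A second reply is that the flowchart of dose advancement (Protocol Figure 6-1) is not shown in the text available and might settle what follows 0 of 3. That limits certainty about the intended decision tree. It does not remove the conflict in the text, where the six-patient requirement, the MTD definition, the Phase 2 gate and the size range all point the same way.

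A third reply is that little depends on the figure. This also stands. A reader might infer that Phase 1b is wrongly sized or less safe than claimed. The documents do not support that either. The cohort size is justified as a safe and conventional choice, and is not derived from the 83%. The 6 to 18 range already fits six patients per dose. The difference is in the conservative direction, because the six-patient rule rejects a toxic dose more often than stated. The escalation wording is editorial, since the de-escalation scheme is explicit elsewhere.

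**Conclusion.** The point holds as a mismatch between a quoted operating characteristic and the plan's acceptance rule, in three places. At a 50% DLT rate the plan quotes 83%, whereas the rule requiring six patients with fewer than 2 DLTs gives 89.1%. The chance of rejecting such a dose is understated by about 6 points. The 3% quoted at a 5% DLT rate stands under either scheme. No patient number, gate or Phase 2 analysis is affected, so this is a minor correction.

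The calculation assumes that DLTs are independent between patients with a common probability, that non-evaluable patients are replaced so that cohorts are complete, and that the six-patient requirement applies to every dose level that is accepted.

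**What to change.** In Protocol 13.1.1, the Protocol synopsis and SAP 5.2.1:

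1. Reconcile the sentence that expands a cohort only at a marginal DLT rate with the requirement for six treated patients, and state what follows 0 DLTs in 3. Check Figure 6-1 against the result.
2. State the probability at a 50% DLT rate for the rule retained: 89% (2 or more DLTs in 6) if six patients are required, as the MTD definition, the Phase 2 gate and the size range imply; 83% only if a dose can clear at 0 of 3, in which case those other statements need revision. The 3% at a 5% DLT rate can stay.
3. Replace the phrase about halting escalation with wording that fits a design that only steps down, for example *the dose would be declared above the MTD*.

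If the six-patient rule is kept, the cost is wording only, with no change to sample size, gates or analyses.

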13.1.2 Expansion Phase

The Expansion Phase will evaluate the efficacy and safety of entinostat when administered at the recommended Phase 2 dose with atezolizumab in a randomized, double-blind, placebo-controlled setting. Up to 70 eligible patients with metastatic TNBC will be randomized to receive atezolizumab with entinostat or placebo in a 1:1 allocation.

The true median PFS for patients with aTNBC receiving atezolizumab monotherapy is expected to be approximately 4 months from the initiation of such treatment. It is hypothesized that the combination of entinostat and atezolizumab will improve true median PFS by 3 months (i.e., from 4 to 7 months). Under the exponential distribution, such an improvement in median PFS represents a reduction of 43% for the true PFS failure hazard rate or equivalently, a hazard ratio of 0.57. Inferential comparisons will be performed using a stratified log-rank test, stratifying on the randomization stratification factor of geographic location. Total information of 60 PFS failures, defined as documented progressive disease by RECIST 1.1 or death due to any cause

without documented progressive disease beforehand, is estimated to provide 80% power to detect a 43% reduction in the PFS failure hazard rate with 1-sided significance level of 0.1 (SEQDESIGN procedure, SAS version 9.2).

Assuming approximately 9 months of accrual and an additional 9 months of follow-up, total accrual of 70 patients (approximately 35 per treatment arm) is projected to result in 60 PFS failures within approximately 18 months of the first patient randomization. Patients who discontinue study treatment for reasons not due to documented progressive disease by RECIST 1.1 will continue to undergo disease assessments until the earlier of documented progressive disease, death, or withdrawal of consent/lost to follow-up. It is anticipated that the number of patients who will drop out of the study without PFS failure beforehand will be low (2–3%). Depending on the actual number of such dropouts, the number of patients accrued may be increased by 6–10 additional patients to accommodate for a higher-than-expected number of dropouts.

13.2 Phase 2 Interim Efficacy Analyses

The sample size and number of PFS failures were adjusted using the O'Brien -Fleming group sequential procedure to account for 1 planned interim analysis of PFS after 45 events (75% information). It is projected that 75% and 100% of total information will be reported at approximately 12 and 18 months, respectively.

The interim analysis will be performed to support the Sponsor's product development plans and ongoing resourcing activities. Although there are no plans to terminate the study early because of early evidence of superior efficacy for the combination treatment, the significance levels at the interim analysis and final analysis will be adjusted to maintain control of the overall type I error rate for multiple testing of PFS (O'Brien 1979).

13.3 Populations for Analysis

The Full Analysis Set (FAS) will serve as the primary population for the analysis of PFS and other efficacy-related endpoints in the Phase 2 portion of the study. The FAS will include all patients who undergo randomization, irrespective of the actual receipt of study treatment.

Patients will be grouped for analysis according to the treatment arm to which they were randomized.

The Per-protocol Analysis Set is for various supportive analyses that may be performed; this excludes patients with important deviations that may substantially affect the results of the primary efficacy analyses. The final determination on protocol violations, and thereby the composition of the per-protocol set, will be made prior to locking the clinical database will be documented in a separate memo.

The Safety Analysis Set will be used for the analysis of safety data in both the Phase 1b and Phase 2 portions of the study. The safety population will consist of all patients who receive at least 1 dose of either entinostat or atezolizumab. At least 1 laboratory or other safety-related assessment subsequent to at least 1 dose of entinostat and atezolizumab is required for inclusion in the analysis of a specific safety parameter. To assess change from baseline, a baseline measurement is also required.

A patient that experiences an AE meeting DLT criteria during Cycle 1 or who receives the full dose of atezolizumab and all doses of entinostat during Cycle 1 without experiencing a DLT, is considered a DLT-evaluable patient.

13.4 Study Endpoints

The primary endpoint of the Phase 1b Dose Determination portion of the study is the recommended Phase 2 dose as assessed by incidence of DLT and overall tolerance.

The endpoints of the randomized Phase 2 Expansion portion of the study are as follows:

Primary Efficacy

- PFS, as determined by the local investigator using RECIST 1.1

Secondary Efficacy

- PFS as determined by irRECIST
- ORR (CR or PR), by RECIST 1.1 and irRECIST

- CBR (CR, PR, or SD for at least 24 weeks)
 - OS
 - TTR and DOR (in patients who experience a best overall response of CR or PR)

Safety

- AEs, clinical laboratory parameters, vital signs, physical exams

Exploratory:

13.5 Statistical Methods

13.5.1 General

The statistical analyses performed for this study will be presented by study phase. For the Dose Determination phase, tabulations will be provided by dose cohort and overall. For the expansion phase, tabulations will be provided by treatment arm. Some analyses may be performed based on both phases combined.

The statistical analyses will be performed using SAS® version 9.2 or later (SAS Institute Inc, Cary NC). Programming specifications will be prepared which describe the datasets and variables created for this study. The datasets will be prepared using the most recent version of CDISC's Study Data Tabulation Model (SDTM) and Analysis Dataset Model (ADaM). The

source SDTM and ADaM datasets from which a statistical analysis is performed (including interim reviews) will be archived with the Sponsor.

13.5.2 Patient Disposition

The number of patients included in each analysis set will be summarized, along with the reason for any exclusions. Patients discontinuing from study treatment and/or withdrawing from study participation the primary reason for discontinuation will be summarized.

13.5.3 Demographics and Characteristics

Descriptive summaries of demographic and screening characteristics will be tabulated for each study phase.

13.5.4 Extent of Exposure

The overall duration of study treatment administration and number of cycles initiated will be tabulated for each patient and summarized for each study phase. For each patient, the cumulative doses administered (in mg) of both entinostat and atezolizumab will be calculated. These data will be further summarized for each dose cohort (or treatment arm) by calculating the mean, standard deviation, median, and range of these values. The number and proportion of patients with one or more dose modifications (i.e., reduction or delay) will be tabulated along with the reason for modification.

13.5.5 Efficacy Analyses

Efficacy analyses will be conducted using the Full Analysis Set and, where appropriate, the Per-protocol Set. With the exception of PFS, all hypothesis testing will be assessed using a one-sided significance level of 0.1. The Lan-DeMets alpha spending function with an O'Brien-Fleming type boundary will be used to control the overall type I error for multiple testing of PFS. The boundary will be derived based on the actual number of PFS failures reported for each analysis.

The primary efficacy endpoint is duration of PFS, defined as the number of months from randomization to the earlier of progressive disease or death due to any cause. Disease assessments will continue until progressive disease, even after the originally assigned study treatment is discontinued. For purposes of analysis, one month is considered 30.4375 days.

The duration of PFS will be summarized descriptively using the Kaplan-Meier method with 95% confidence intervals calculated using Greenwood's formula. Inferential comparisons between treatment arms will be made using the stratified log rank test, stratifying on the randomization stratification factor of geographic location. Estimation of the hazard ratio for treatment effect and its corresponding 95% confidence interval will be determined using a stratified Cox proportional hazards model, without any other covariate. Homogeneity in the hazard ratios between randomization strata will be examined by Wald's test. The corresponding results without stratification will be reported as supplemental analyses. The adequacy of the Cox model will be evaluated, including an assessment of the proportional hazards assumption ([Therneau 2000](#)).

For the interim and primary analyses, PFS will be right-censored for patients who meet one or more of the following conditions:

- Patients with no screening or post-screening disease assessments unless death occurred prior to the first planned assessment (in which case the death will be considered a PFS event)
- Patients who initiate subsequent anticancer therapy in the absence of documented progression
- Patients who die or have progressive disease after missing 2 or more consecutively scheduled disease assessment visits
- Patients who are last known to be alive and progression-free on or before the data cut-off date

For such patients, the progression or censoring date will be determined based on described conventions ([FDA 2007](#)). Sensitivity analyses will be performed to assess the impact of the different censoring mechanisms and deviations from the planned schedule of disease assessments ([Bhattacharya 2009; Stone 2011](#)).

ORR will be estimated based on the crude proportion of patients in each treatment arm whose best overall response during the course of study treatment is CR or PR. Tumor response will be assessed using irRECIST. Approximate 95% confidence intervals will be calculated by treatment arm for the true ORR. The inferential comparison of the observed ORRs will be made using the Cochran-Mantel-Haenszel chi-square test, stratified by the randomization stratification factors. The corresponding results without stratification will be reported as supplemental analyses.

DOOR will be calculated for patients who achieve CR or PR. For such patients, DOOR is defined as the number of months from the start date of PR or CR (whichever response occurs first) and subsequently confirmed, to the first date that recurrent or progressive disease is documented. The date of progression or censoring for DOOR will be determined using the conventions described for PFS. DOOR will be summarized descriptively for each treatment arm using the Kaplan-Meier method. Inferential comparisons between treatment arms for DOOR are not planned.

CBR will be estimated based on the crude proportion of patients in each treatment arm whose best overall response during the course of study treatment is CR, PR, or stable disease lasting for at least 24 weeks. Stable disease will be measured from the start date of study treatment until the criteria for progressive disease is first met. The analysis of CBR and its duration will be based on the methods described above for ORR and DOOR, respectively.

OS is defined as the number of months from randomization to the date of death (due to any cause). Patients who are alive or lost to follow-up as of a data analysis cutoff date will be right-censored. The censoring date will be determined from the patients' date of last contact or data analysis cutoff date, whichever date occurs first. The analysis of OS will be based on the methods described above for PFS.

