5.4.2 Phase 2 Expansion Phase

The following analyses are planned:

- An interim safety analysis will be performed following the completion of Cycle 1 for the first 20 patients enrolled in the Phase 2 expansion phase, and will utilize a Data Safety Monitoring Board (DSMB).
- An interim efficacy analysis will be performed when 45 PFS events have observed. Data cut-off for the analysis will be based on the calendar date of the 45th PFS event (per RECSIT 1.1). Safety and secondary endpoints will also be evaluated. The same data cut-off used for the PFS analysis is also used for the corresponding analysis of safety and secondary endpoints.
- Primary efficacy analysis will be performed when 60 PFS events are observed. Similarly, the data cut-off for the primary analysis will be based on the calendar date of the 60th PFS event. Safety and secondary endpoints will coincide with the primary PFS analysis.
- End of study analysis for safety and OS analysis will be performed when the last patient terminates study treatment.

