6.3 Clinical Benefit Rate (CBR)

CBR is estimated based on the crude proportion of patients in each treatment arm whose best overall response during the course of study treatment is CR, PR or SD lasting for at least 24 weeks (measured from the date of randomization to the last date where SD is reported).

$$CBR_{RECIST\ 1.1} = \frac{\# \text{ of patients with best confirmed overall response as CR/PR/ SD lasting for} \geq 24 \text{ weeks}}{\text{Total number of patients}}$$

Similarly, CBR is calculated based on irRECIST as below:

$$CBR_{irRECIST} = \frac{\# \text{ of patients with best confirmed overall response as irCR/irPR/irSD lasting for} \geq 24 \text{ weeks}}{\text{Total number of patients}}$$

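### ORR, CBR, OS and irRECIST PFS are analysed two or three times at an unadjusted one-sided 0.1 with no formal look named, and the interim CBR is immature

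*Protocol*

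**What the plan says.** **Level of the tests.** Protocol 13.5.5: "With the exception of PFS, all hypothesis testing will be assessed using a one-sided significance level of 0.1". The sentences that follow provide for repeated looks at PFS only: "The Lan-DeMets alpha spending function with an O'Brien-Fleming type boundary will be used to control the overall type I error for multiple testing of PFS" and "The boundary will be derived based on the actual number of PFS failures reported for each analysis". Protocol 13.2 describes the adjustment made to "account for 1 planned interim analysis of PFS after 45 events (75% information"), and 13.1.2 sets the final analysis at "Total information of 60 PFS failures", with failure defined by RECIST 1.1 or death.

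**Number of looks.** SAP 5.4.2 says of the 45-event interim: "Safety and secondary endpoints will also be evaluated". It places the secondary endpoints alongside the primary PFS analysis at 60 events as well. It then adds: "End of study analysis for safety and OS analysis will be performed when the last patient terminates study treatment".

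**Which endpoints are compared between arms.** ORR has a stratified Cochran-Mantel-Haenszel comparison, CBR follows the ORR methods, and OS follows the PFS methods (protocol 13.5.5; SAP 10.8.2 to 10.8.4). The planned tables in SAP 11.1 for PFS (both criteria), ORR and CBR include treatment comparisons. DOR and TTR have none (SAP 10.8.5).

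**CBR.** SAP 6.3 defines it as the "crude proportion of patients in each treatment arm whose best overall response during the course of study treatment is CR, PR or SD lasting" at least 24 weeks from randomization, divided by all patients. Neither document sets a minimum follow-up.

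**The concern.** Protocol 13.2 adjusts the PFS levels even though no early stop for superiority is planned, so the sponsor accepts that two tests of one endpoint need control whether or not the trial can stop. The same reasoning applies to ORR, CBR and OS, for which nothing is provided. Read literally, the plan produces two p-values for ORR and CBR and up to three for OS, each judged at 0.1, and does not say which one counts. The interim serves the sponsor's development and resourcing decisions, so a favourable secondary p-value there could carry weight.

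Two further gaps follow from the same sections. irRECIST PFS is a secondary endpoint that also bears the name PFS, and the text does not say whether the exception covers it. And an all-patient CBR computed about three months after the last patient is randomized counts some patients as failures only because 24 weeks have not yet passed.

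**Working it through.** **1. The plan's own figure.** Inputs from protocol 13.1.2 and 13.2: medians 4 and 7 months (HR 4/7 = 0.571), one-sided 0.1, 80% power, one interim at 45/60 = 0.75.

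- Fixed design (Schoenfeld): 4(1.2816 + 0.8416)² / (ln 0.571)² = 18.03 / 0.3132 = 57.6, so 58 events.
- With a two-look O'Brien-Fleming boundary, 59.6 events are needed, and 60 events give power 0.802.
- With Lan-DeMets spending the figures are 59.7 events and 0.801, with nominal one-sided levels of 0.0575 at the interim and 0.0839 at the final.

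The stated 60 events and 80% power reproduce. The primary analysis is sound on this point.

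**2. Unadjusted repeated looks.** Under the null, the chance that at least one look exceeds z = 1.2816 is 1 − P(all Zᵢ ≤ 1.2816), with Z multivariate normal and corr(Zᵢ, Zⱼ) = √(tᵢ/tⱼ) for information fractions tᵢ < tⱼ.

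| Endpoint | Information fractions | Source of fractions | Chance of a false positive at any look |
|---|---|---|---|
| irRECIST PFS, if outside the exception | 0.75, 1 | PFS fraction in 13.2 (assumed to carry over) | 0.136 |
| ORR | 0.90, 1 / 0.95, 1 | assumed | 0.122 / 0.116 |
| OS, three looks | 0.80, 0.90, 1 | assumed | 0.141 |
| OS, three looks | 0.70, 0.85, 1 | assumed | 0.152 |
| OS, three looks | 0.50, 0.75, 1 | assumed | 0.171 |
| OS, three looks | 0.30, 0.50, 1 | assumed | 0.191 |

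The irRECIST PFS figure moves little with the fraction: 0.143 at 0.65 and 0.1275 at 0.85. If the endpoint falls inside the exception and is spent like PFS, it is about 0.10. A simulation of ORR (assumed rates 10–30% and assumed response times, interim at month 12) gave 0.115–0.123, in line with the table.

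The documents give no OS median, death count or end-of-study date. With exponential OS, assumed medians of 8 to 24 months, looks at 12 and 18 months and a last look at 21 to 48 months, the three-look figure was 0.158 to 0.195.

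**3. CBR at the interim.** Inputs: uniform accrual over 9 months (9 months is in 13.1.2; uniformity is assumed), exponential PFS with medians 4 and 7 months, 35 per arm, interim at about month 12 (13.2). 24 weeks = 168 / 30.4375 = 5.52 months.

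- Short of 24 weeks at month 12: (9 − (12 − 5.52)) / 9 = 28%, about 20 of 70. At month 13: 17%, about 12 of 70.
- Short of 24 weeks **and** event-free at month T: (e^(−λ(T−9)) − e^(−5.52λ)) / (9λ), with λ = ln 2 / median.
 - Month 12, control: (0.5946 − 0.3843) / 1.560 = 0.135, or 4.7 of 35.
 - Month 12, combination: (0.7430 − 0.5789) / 0.891 = 0.184, or 6.4 of 35.
 - Total about 11 of 70. At month 13: 2.6 + 3.7, about 6 of 70.
- This model gives 42.2 events at month 12 and 45.5 at month 13, so the 45th event may fall nearer month 13 than the projected month 12.
- Effect on the comparison, taking event-free at 24 weeks as a stand-in for CBR and ignoring early responders: with full follow-up 38% and 58%, a gap of about 20 points. Observable at month 12: 38.4% × 0.72 = 28% and 57.9% × 0.72 = 42%, a gap of 14 points.

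A confirmed responder counts as benefit before 24 weeks, so the shortfall is somewhat smaller than these figures.

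**The case against.** The strongest reply is that 0.1 is the level of each test, and that the plan claims overall control for PFS only. No sentence allows a secondary endpoint to be declared positive at the interim. SAP 5.4.2 speaks of evaluating the endpoints there, not of testing them. If one analysis were named as the formal one, the error would be 0.1. For OS, three formal tests are not explicit, because the planned OS table is only a summary by treatment group although SAP 10.8.4 applies the PFS methods. These are also secondary endpoints in a 70-patient phase 2 trial.

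Much of this stands, and it rules out several readings that a reader might infer:

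- That every secondary endpoint is tested at every look. DOR and TTR are not compared at all, and only OS has a third analysis.
- That the true error simply is 0.14 or more. The higher figures need the condition that success at any look may be claimed.
- That 0.14 for irRECIST PFS is settled. The exception names PFS without qualification. Against that reading, the failures that drive the boundary are defined by RECIST 1.1, and irRECIST PFS is listed as secondary.
- That the OS range is a property of the trial. It rests on fractions the documents do not supply.
- That CBR cannot be evaluated at the interim, or that 28% of patients are miscounted. Many of those 20 will already have progressed or died and are rightly failures.

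The reply does not remove the gap. The methods sections prescribe comparative tests, nothing limits the interim to description, and where the sponsor wanted no comparison (DOR and TTR) the SAP says so.

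**Conclusion.** The point holds in a conditional form. ORR, CBR, OS and irRECIST PFS carry an unadjusted one-sided 0.1 over two looks (three for OS), with no look named as the formal one. If any look may be claimed, the false-positive chance is about 0.12 for ORR, about 0.14 for irRECIST PFS under one of two readings, and about 0.14–0.19 for OS over assumed fractions from 80/90/100% to 30/50/100%. No separate figure was calculated for CBR, because its interim problem is mainly immaturity. It is biased low in both arms, with about 11 of 70 patients at month 12 (about 6 at month 13) event-free but short of 24 weeks, and the arm gap shrinks. That result assumes uniform accrual and the plan's exponential medians.

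The documents do not support the stronger inference that the sponsor plans to pick whichever look is favourable; they only leave it open. The primary PFS analysis is unaffected. This should be corrected but does not threaten the trial's main conclusion.

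**What to change.** In SAP 5.4.2 and 10.8:

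- At 45 events, report secondary endpoints descriptively, with estimates and intervals and no tests. Omit CBR, or limit it to patients randomized at least 24 weeks before the cut-off.
- Name the 60-event analysis as the single formal test for ORR, CBR and irRECIST PFS.
- Name one formal OS analysis, or give OS its own spending function based on deaths.
- State whether the PFS exception in protocol 13.5.5 covers irRECIST PFS.

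If repeated tests are wanted, the levels must fall. Two looks at 0.75 and 1 need 0.072 at each look to hold 0.1 overall. Three OS looks need a constant level between 0.048 (assumed fractions 0.3/0.6/1) and 0.064 (0.7/0.9/1).

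The cost is SAP wording and the loss of interim p-values on secondary endpoints. No patients, visits or events are added.
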